#### 3.2 Serious Adverse Event Reporting

By definition, an Adverse Event is defined as a Serious Adverse Event (SAE) according to the following criteria:

- Death.
- Life-threatening (i.e. results in an immediate risk of death).
- Requires inpatient hospitalization or prolongation of existing hospitalization.
- Permanent or significant disability/incapacity.
- Gives rise to a congenital anomaly/birth defect, or cancer, or any experience that suggests a significant hazard, contraindication, side effect, or precaution that may require medical or surgical intervention to prevent one of the outcomes listed above.
- Event occurring in a gene therapy study.
- Event that changes the risk/benefit ratio of a study.
- Any other event the Principal Investigator judges to be serious or which would

suggest a significant hazard, contraindication, side effect, or precaution.

Serious Adverse Event reporting will be in accordance with the UCSF IRB Regulations and Code of Federal Regulation Title 21 Part 312.32. The SAE will be reported on a Med Watch form.

UCSF IRB website for guidance in reporting serious adverse events:

<https://irb.ucsf.edu/adverse-event>

FDA website for guidance in reporting serious adverse events:

[www.fda.gov/Safety/MedWatch/HowToReport/default.htm](http://www.fda.gov/Safety/MedWatch/HowToReport/default.htm)

Med Watch forms and information:

[www.fda.gov/medwatch/getforms.htm](http://www.fda.gov/medwatch/getforms.htm)

All Serious Adverse Events are entered into OnCore®, as well as submitted to the IRB (per IRB guidelines) via iRIS®. All SAEs, whether expected or unexpected, must be reported to the UCSF Coordinating Center within 1 business days of becoming aware of the event. The SAEs are reviewed and monitored by the UCSF Data and Safety Monitoring Committee on an ongoing basis and discussed at DSMC meetings, which take place every six weeks. The date the SAE was sent to all required reporting agencies will be documented in OnCore®.

If a death occurs during the treatment phase of the study or within 30 days after the last administration of the study drug(s) and is determined to be possibly, probably, or definitely related either to the investigational drug or any research related procedure, the Study Chair at the UCSF Coordinating Center or the assigned designee must be notified within 1 business day from the participating site(s) and the Study Chair must then notify the DSMC Chair or qualified alternate within 1 business day of this notification. The reporting procedure is by communication via phone or in person with written documentation of the one-on-one communication via e-mail, with a copy of the e-mail to the DSMC Manager.

### **3.3 Review of Adverse Event Rates**

If an increase in the frequency of Grade 3 or 4 adverse events (above the rate reported in the Investigator Brochure or package insert) is noted in the study, the Study Chair at the UCSF Coordinating Center is responsible for notifying the DSMC at the time the increased rate is identified. The report will indicate if the incidence of adverse events observed in the study is above the range stated in the Investigator Brochure or package insert.

If at any time the Study Chair stops enrollment or stops the study due to safety issues, the DSMC Chair and DSMC Manager must be notified within 1 business day and the IRB must be notified within 10 business days via an iRIS Reporting Form.

**Appendix 5 Prohibited Medications**

---

|                             |
|-----------------------------|
| Medications to Avoid |
|-----------------------------|

|  |
|--|
| CC# pending: A Phase II Trial to Evaluate Trametinib in Molecular subpopulations of patients with advanced non-small cell lung cancer |
|--|

The following is a list of medications to avoid while you are participating in this study. If you go to any medical visit, please take this list with you for the doctor's reference.

Before you begin treatment, [name] or one of his associates will review all medications you are taking. Make sure you talk with [name] before you start or stop taking any medications. This list contains only the most common drugs that are known to interact with the drugs used in this study. It is very important to discuss all medications that you are taking with your study doctor. This information will be reviewed at each study visit.

| Strong inducers of CYP3A or CYP2C8 |   | Strong inhibitors of CYP3A |                          |
|------------------------------------|---|----------------------------|--------------------------|
| Generic Name                       | Brand Names ®                             | Generic Name               | Brand Names ®            |
| Rifampin                           | Rifadin                                   | Clarithromycin             | Biaxin                   |
| Rifabutin                          | Mycobutin                                 | Telithromycin              | Ketek                    |
| Rifapentine                        | Priftin                                   | Troleandomycin             |                          |
| Carbamazepine                      | Tegretol, Carbatrol, Equetro              | Nefazodone                 | Serzone                  |
| Oxcarbazepine                      | Trileptal                                 | Itraconazole               | Sporanox, Onmel          |
| Phenobarbital                      |   | Ketoconazole               | Nizoral, Xolegel, Extina |
| Phenytoin                          | Dilantin, Phenytek, Dilantin-125, Cerebyx | Posaconazole               | Noxafil                  |
| s-mephenytoin                      |   | Voriconazole               | Vfend                    |
| Bosentan                           |   | Ritonavir                  | Norvir                   |
| St. John's Wort                    |   | Saguinavir                 |                          |
|                                    |   | Atazanavir                 | Reyataz                  |
|                                    |   | Gemfibrozil                | Lopid                    |
|                                    |   | Conivaptan                 | Vaprisol                 |

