**Abstract**

|                      |  |
|----------------------|--|
| Title                | Phase II trial to evaluate trametinib in patients with advanced NF1 -mutant non-small cell lung cancer  |
| Patient population   | Patients with metastatic or unresectable locally advanced non-squamous, non-small cell lung cancer (NSCLC) whose tumors harbor a non-synonymous NF1 mutation, with progressive disease on at least one prior line of therapy.   |
| Rationale for Study  | 
NF1 is a tumor suppressor gene, which encodes a RAS GTPase activating protein (GAP), which facilitates the hydrolysis of RAS-GTP to the inactive RAS-GDP. Germline NF1 inactivating mutations are associated with both pediatric and adult malignancies. Somatic mutations in NF1 have been associated with adenocarcinoma of lung, malignant melanoma, glioblastoma, as well as myelodysplastic syndrome. NF1 loss in melanoma cell lines that were wild-type for BRAF/RAS resulted in elevated RAS-GTP levels and MAPK signaling activation. Treatment of these cells with the MEK inhibitor trametinib resulted in sustained ERK inhibition and suppression of tumor cell proliferation. Likewise, leukemias have been shown to arise from either germline or somatic loss of NF1 and treatment of autochthonous myeloid malignancies driven by engineered NF1 loss in the mouse have been shown to be sensitive to MEK inhibition in preclinical models.
 
We hypothesize that patients with advanced NSCLC whose tumors harbor non-synonymous somatic mutations in NF1 will exhibit tumor dependence upon the MAPK signaling pathway and will be sensitive to treatment with the potent and selective MEK inhibitor trametinib.
 |
| Primary Objective    | To evaluate the efficacy of trametinib in patients with advanced, non-squamous NSCLC who have progressed on at least one prior line of systemic cancer therapy (i.e. platinum doublet, anti-PD1/PDL1 or appropriate EGFR, ALK, or ROS-1 targeted therapy), and whose tumors harbor a non-synonymous mutation in NF1 and is negative for an activating mutation in KRAS .   |

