### 1.4.3 Patient-derived xenografts and organoids

When possible, patient derived xenografts or organoids will be generated from patient biopsy specimens. Alterations discovered in the clinical specimen analysis will be functionally studied using our standard cell-based assays. We will test if activation or suppression of the candidate resistance gene (as indicated by whether the gene is increased or decreased in resistance)

promotes MEK inhibitor resistance, in vitro and in vivo in tumor xenograft and organoid studies.

*Version date: 02-15-2018*

*Protocol CC#: 166521*

---

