## 6.4 Prohibited Medications

All treatments that the investigator considers necessary for a subject's welfare may be administered at the discretion of the investigator in keeping with the community standards of medical care. Palliative and supportive care is permitted during the course of the trial for underlying medical conditions and management of symptoms. Surgery or radiotherapy for tumor controls not permitted during the study; however, radiotherapy or procedures for symptom management is allowed.

Subjects are prohibited from receiving antineoplastic systemic chemotherapy or biological therapy not specified in this protocol.

Bisphosphonates or denosumab are allowed for patients with bone metastases.

Growth factor support may be considered for patients with neutropenia after discussion with the study PI.

Avoid concurrent use of strong CYP3A inhibitors during treatment.

Medications known to produce QT prolongation should be avoided during treatment of patients with and trametinib. See <http://crediblemeds.org/> for the most up-to-date reference lists of QT-prolonging medications. Please note that the lists contain common supportive medications, such as anti-emetics (ondansetron [and other 5HT3 antagonists], metoclopramide, hydroxyzine), antibiotics (azithromycin, ciprofloxacin, metronidazole) and anti-depressants (escitalopram).

Medications to consider for nausea that are not associated with QT prolongation include:

- Steroids (dexamethasone, methylprednisolone)
- Benzodiazepines
- Aprepitant
- Select anticholinergic agents (scopolamine)
- Trimethobenzamide
- Cannabinoids

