#### Interim Analyses and Stopping Rules

Using a Simon 2-stage design, if we do not observe at least 2 responses within the first 15 patients in a given cohort, enrollment to that arm would be stopped due to lack of efficacy.

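### The Appendix 5 page that patients carry to medical visits gives no QT warning, although Section 6.4 says QT-prolonging drugs should be avoided

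*Combined protocol and SAP*

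**What the plan says.** Section 6.4 (Prohibited Medications) states: "Medications known to produce QT prolongation should be avoided during treatment of patients with and trametinib". A word has evidently dropped out, but the sense is plain. The section links to an online QT reference and warns that its lists include common supportive drugs, "such as anti-emetics (ondansetron [and other 5HT3 antagonists], metoclopramide, hydroxyzine), antibiotics (azithromycin, ciprofloxacin, metronidazole) and anti-depressants (escitalopram". It then gives six options for nausea that are not associated with QT prolongation. It also tells investigators to avoid strong CYP3A inhibitors. It does not mention CYP inducers and does not refer to Appendix 5.

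Appendix 5 has the same title and is written to the patient: "If you go to any medical visit, please take this list with you for the doctor's reference". It limits its own scope: "This list contains only the most common drugs that are known to interact with the drugs used in this study". It asks patients to check with the study doctor before a drug is started or stopped. Its table has two groups, strong inducers of CYP3A or CYP2C8 and strong inhibitors of CYP3A.

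The page is headed "CC# pending: A Phase II Trial to Evaluate Trametinib in Molecular subpopulations of patients with advanced non-small cell lung cancer". The Abstract gives the title as "Phase II trial to evaluate trametinib in patients with advanced" NF1-mutant NSCLC, and the protocol's page header reads "Protocol CC#: 166521".

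**The concern.** The page is meant to be shown to a doctor who treats the patient outside the trial and is unlikely to have Section 6.4 to hand. Such a doctor would reasonably take a list under this title as the trial's list of drugs to avoid. The doctor would see CYP agents and nothing about QT.

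The protocol takes QT seriously elsewhere. Prolonged QTc is an event of special interest in Sections 5.2 and 5.3, and exclusion criterion 13 bars a baseline QTcB of 480 msec or more. By contrast, Sections 1.2.3 and 6.2 describe the drug-interaction potential of trametinib as low. The page therefore covers the risk that the protocol plays down and leaves out one that it monitors.

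Six of the seven drugs named in Section 6.4 are anti-emetics or antibiotics, which an outside doctor might well prescribe to a patient with nausea, diarrhea or infection. What is at stake is an avoidable prescription of a drug that the protocol says to avoid. No estimate or test in the trial depends on it.

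**Working it through.** No statistic is involved. The check is a side-by-side reading of Section 6.4 and Appendix 5.

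**Drugs on the Appendix 5 page**

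- Inducers (10): rifampin, rifabutin, rifapentine, carbamazepine, oxcarbazepine, phenobarbital, phenytoin, s-mephenytoin, bosentan, St. John's Wort.
- Inhibitors (13): clarithromycin, telithromycin, troleandomycin, nefazodone, itraconazole, ketoconazole, posaconazole, voriconazole, ritonavir, saquinavir (misspelled on the page), atazanavir, gemfibrozil, conivaptan.
- Total: 10 + 13 = 23.

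**QT examples in Section 6.4, looked up on the page**

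| Type | Named in 6.4 | On the page |
|---|---|---|
| Anti-emetic | ondansetron, metoclopramide, hydroxyzine | 0 of 3 |
| Antibiotic | azithromycin, ciprofloxacin, metronidazole | 0 of 3 |
| Anti-depressant | escitalopram | 0 of 1 |
| All | 3 + 3 + 1 = 7 | 0 of 7 |

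The page also lacks a QT group, the QT web link, any mention of 5HT3 antagonists as a class, and the nausea alternatives. The gap does not come from removed text: the table is complete as printed and Appendix 6 follows it directly.

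**The reverse comparison.** Of the page's two groups, Section 6.4 covers only the strong CYP3A inhibitors. The 10 inducers have no counterpart there, so the two texts differ in both directions.

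**Heading.** The number on the page is still pending, where the protocol carries 166521. The title refers to molecular subpopulations, where the current title is specific to NF1. Cohort language also survives in the statistical section, for example in the stopping rule: "in a given cohort, enrollment to that arm would be stopped due to lack of efficacy". That suggests the page was carried over from a broader multi-cohort version of this protocol, but this is an inference.

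**The case against.** The best defence is that the two texts do different jobs. The page presents itself as a short list of common interacting drugs, and both of its groups concern metabolism. The QT advice is a separate precaution that points to a website kept up to date. Both texts can be followed at once, so a reader who infers a contradiction goes too far.

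There are also real safeguards. The page sends patients to the study doctor before any new drug and says that its contents are reviewed at each visit. Concomitant drugs are recorded on Days 1, 8 and 15 of Cycle 1 and in every later cycle. ECGs are scheduled at screening, on Cycle 1 Day 1 and during later treatment. Table 5.9 calls for a review of concomitant drugs when QTc is prolonged.

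Most of this stands, and it is why the point is minor. It does not remove the gap. The first safeguard relies on the patient making the call. From Cycle 2, Table 6.1 marks the concomitant-drug check only on Day 1 of a 28-day cycle, so a short outside course could begin and end between checks. The Table 5.9 review comes after prolongation has been found.

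It is also fair to say that the printed page may not be the handout in use. Under Appendix 3, patient handouts are filed separately, and the consent pages were not available for this review. The point therefore concerns Appendix 5 as printed, not everything that patients are told.

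**Conclusion.** The point holds as a minor omission. Section 6.4 names seven QT-prolonging drugs to avoid, and the page that patients carry names none of them and gives no QT warning. The stale heading alone would be clerical, but it belongs in the same correction.

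A reader might infer more in three ways, and the documents support none of them.

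- **That whole drug classes are missing.** They are not. On ordinary drug knowledge, the page includes antibiotics (such as clarithromycin and rifampin) and an anti-depressant (nefazodone), listed as CYP agents. What is missing is the seven named drugs and any QT label.
- **That the number of patients affected can be estimated from the side-effect rates.** Section 4.1 puts nausea and diarrhea at 20% or more in the melanoma safety set. Those are adverse-reaction rates, not prescribing rates, and still less rates of outside prescribing. Table 5.6 makes oral antibiotics conditional on the duration or clinical course of the diarrhea, and it guides study investigators, who have Section 6.4.
- **That QT harm or lost dosing follows.** The documents give no rate of QTc prolongation, and the cardiac reactions in Section 4.1 do not include it. The QTc dosing rules in Tables 5.9 and 5.14 have conditions of their own and are a separate matter.

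The risk is therefore unquantified and, given the safeguards, probably small. The conclusion assumes that the page is used as printed. The primary analysis is not affected.

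**What to change.** Revise Appendix 5 in one edit:

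1. Add a QT-prolonging section using material already in Section 6.4: the seven drugs as examples, other 5HT3 antagonists, the reference link, and the nausea options not associated with QT prolongation.
2. Replace the heading with the current NF1 title and CC# 166521.
3. In Section 6.4, refer to Appendix 5 and state whether the CYP3A/CYP2C8 inducers on the page are also to be avoided. Without that statement, the cross-reference would bring in a restriction that Section 6.4 does not make or explain.

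The cost is one revised page and a sentence or two in Section 6.4. Section 9.4 requires PRC and IRB approval for an amendment, and the participating sites would need the new page. Sample size, visits and analysis stay as they are.

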## **Appendix 6 Specimen Collection**

### **Sampling and shipping information**

For the purposes of this study, a whole blood sample is collected by standard phlebotomy procedures. Blood should be drawn in the morning prior to drug administration. Aliquots of 5-10 ml of venous blood will be drawn from each patient using PPT and SST vacutainers and or PAXGene tubes.

- 1) Two Plasma Preparation (EDTA) Tubes (PPT, 6-10ml)
- 2) One Serum Separator Tube (SST, 8.5ml)
- 3) In cases in which sequencing to be performed immediately by the [name] lab, one PAXGene tube will be collected for transport

These samples will be used by the clinical coordinator to generate:

- 1) 6 x 300 µl of plasma aliquots, frozen at -80° Celsius
- 2) 6 x 300 µl of sera aliquots, frozen at -80° Celsius
- 3) 4 x 1.5ml whole blood aliquots, frozen at -80° Celsius
- 4) Two “Crude Buffy Coat” aliquots

Processing of the samples will be carried out using following protocols:

#### Plasma and Crude Buffy Coat Preparation SOP

- Gently inverts the Plasma Preparation Tube 8 -10 times following venipuncture
- The sample will be hold at room temperature (RT) until processing. Processing should occur within 2 hours of the blood draw.
- The sample will be centrifuged at 1,100 x g for 10 minutes at RT in a swing out rotor.
- Plasma aliquots will be transferred from the vacutainer to cryo vials
- Plasma samples will be frozen and archived at -80C° Celsius.
- The “Crude” Buffy Coat is removed with a transfer pipette and two equal aliquots are generated in 1.8 ml cryovial.
- The cryo vials are immediately placed in a –80° Celsius freezer (no transfer in slow freezing chamber).
- The clinical coordinator transfers samples into a Tissue Core–80° Celsius freezer for temporary storage, the time when the samples have been frozen will be noted.

### Serum Preparation SOP

- Inverts the Serum Preparation Tube 5 times following venipuncture and records the blood draw time
- Hold sample at room temperature. Wait for blood to clot 30 - 45 minutes after blood collection in order to ensure that proper blood clotting occurred. Blood processing should occur within 2 hours of blood draw.
- Centrifuge at 1,100 x g for 10 minutes at room temperature in a swing out rotor.
- Serum aliquots will be transferred from the vacutainer to the cryo vials using a 200 µl transfer pipette.
- Serum samples will be frozen and archived at -80° Celsius.

### Whole Blood Preparation SOP

- The EDTA tube is inverted 5 – 10 times before 4 x 1500 µl aliquots are transferred into 1.8 ml cryo vials.
- The vials are immediately placed in a -80° Celsius freezer (no transfer in slow freezing chamber).

### PaxGene tube Blood Preparation SOP

- The PaxGene tube is inverted 5 – 10 times.
- The tube is stored at room temperature for up to 2 hours.

If not picked up or delivered to the [name] lab within 2 hours, the tube is temporarily stored at – 20 Celsius freezer for up to 72 hours

### **Sample shipment instructions**

For each shipment, an inventory of the samples should accompany the shipment. This inventory should include the study ID, subject ID, sample number, visit number scheduled time of collection.

Clearly indicate any missing specimens. The original inventory will be retained at the site in the Investigator's file.

All samples will be kept at the temperature specified up to and during the shipment. Unless instructed otherwise, the samples will be packed carefully with suitable packing material and dry ice to keep them frozen.

All shipments should be sent (Monday through Wednesday **only**) by a carrier guaranteeing overnight delivery. The following items should be considered:

- Advise the carrier of the type of service desired, need for personalized door-to-door pickup, and delivery guaranteed within 24 hours.

- Advise the carrier of the nature of the shipment's contents (human biological specimens) and label the package accordingly.
- Indicate Novartis drug code and Study No. on the face of the parcel to be shipped. The parcel also must carry a "dangerous goods" label because of the dry ice (labels supplied by the courier).
- The carrier must be asked to store the parcel(s) in a freezer if shipment is delayed and to replace exhausted dry ice before transportation continues.

□□

### Please notify the addressee *in advance* of the shipment and indicate:

- Number of the airbill
- The time and date of shipping and approximate time of arrival
- To whom the shipment is addressed, the study number, carrier and the shipping form number (or equivalent airbill number)
- The sender's name, telephone number and alternative contact personnel
- The total number of cartons and unit weight of each carton

Also notify the Clinical Trial Leader ██████████ when a shipment has been scheduled.

